1.2 Prior Clinical Trials

In addition to the above publications, preliminary data is available from a small 10 patient trial conducted with the Fully Covered WallFlex Pancreatic Stent. Patients with painful chronic pancreatitis of Cremer Type IV were enrolled between June and September 2014. Intended indwell was 3 months in 5 patients and 6 months in 5 patients. In total 14 stents

August 28, 2017

Boston Scientific
WallFlex Pancreatic Pivotal Protocol
91067616 Rev/Ver AK
Page 17 of 64

were placed, with 2 patients having immediate removal and replacement of the initial stent due to deployment in unsatisfactory position and 2 patients needing a second stent placement after premature complete distal migration of the first indwelling stent. Stent migration without symptoms, thought to be a reflection of adequate calibration of the benign stricture, occurred in 6 stent placements, not requiring restenting. Clinically meaningful complete distal migration (CDM) with symptoms occurred in 25% (3/12) of stent placements with intended stent indwell. There were no proximal stent migrations. Endoscopic stent removal was performed per-protocol easily in one patient after a 3 month indwell and in 2 patients after a 6 month indwell without stent removal-related adverse events (AEs). After a median follow-up of 196 days (range 175 - 373) after stent removal or observation of CDM of the stent, 80% (8/10) of patients remained stent-free. Longer term follow-up is ongoing. One patient had premature CDM followed by placement of plastic stents. One patient had no pain relief after SEMS placement and had subsequent pancreatic diversion surgery which did not provide pain relief either. Serious Adverse events (SAEs) occurred in 50% (5/10) of patients, with 7 SAEs (2 pain associated with premature CDM, 2 transient pain related to stent expansion immediately following stent placement, 1 pain unresolved by stenting or subsequent pancreatic diversion surgery, 1 bacterial infection and 1 mild acute pancreatitis). No SEMS needed to be removed due to intolerable pain after SEMS placement. There were no stent-induced ductal changes.

1.3 Conclusion

These publications and published expert opinions conclude that the use of fully covered SEMSs (FCSEMSs) is feasible and can be safe and effective for treatment of Cremer type IV benign PD strictures caused by CP.

2 Device Use and Description

2.1 Device Description

Study devices are manufactured by Boston Scientific Corporation. The WallFlex™ Pancreatic RX Fully Covered Soft Stent System consists of a flexible delivery system preloaded with a self-expanding pancreatic metal stent. The stent is made from a metallic radiopaque material that is formed into a cylindrical mesh. The stent is offered fully covered with Permalume™ Coating, a translucent silicone polymer, to reduce the potential for ingrowth through the stent. The stent has a retrieval loop for removal during the initial stent placement procedure. The retrieval loop may be used in the event of incorrect placement and/or removal from benign strictures. The stent has a flare on the duodenal end to prevent migration into the pancreas. The WallFlex™ Pancreatic RX Fully Covered Soft Stent System is provided sterile using ethylene oxide and is a single use device.

The study device is not approved for commercial use. However, the clinical study will be conducted only in countries where the WallFlex Pancreatic Stent is approved for the clinical trial indication for use by the Competent Authority (CA). Local EC (Ethics Committee)/IRB (Institutional Review Board) approval will be obtained at each participating center.

August 28, 2017

Boston Scientific
WallFlex Pancreatic Pivotal Protocol
91067616 Rev/Ver AK
Page 18 of 64

Study devices are labeled on the box and inner pouch and include information not limited to name of legal manufacturer, device name and dimensions, lot number, expiration date and investigational use statement. Device labeling will be provided in local language(s) as per national regulations. Devices will be available in the following matrix:

Table 2.1-1: Clinical UPN (RX, Soft)

Rapid Exchange	Length	Width	
		6mm	8mm
	40 mm	M00577420	M00577480
	50 mm	M00577430	M00577490
	60mm	M00577440	M00577500

For a detailed description of the WallFlex™ Pancreatic RX Fully Covered Soft Stent System, please reference the Investigator's Brochure.

2.2 Device Use

- The WallFlex Pancreatic Stent is intended to facilitate drainage of the pancreatic duct to reduce pain in patients with painful chronic pancreatitis.
- Prior to WallFlex Pancreatic stent placement, the patient must receive/have received an endoscopic pancreatic sphincterotomy (EPS). The EPS can be administered at the time of the stent placement procedure or can have been administered during a prior endoscopic procedure.
- Investigators in this trial should be experienced with pancreatic endotherapy.

3 Primary Objective

To prospectively document the performance of a FCSEMS for treatment of pancreatic duct strictures in patients with painful chronic pancreatitis.

4 Endpoints and Study Design

4.1 Primary Effectiveness Endpoint

Pain Reduction

Pain reduction will be assessed at 6 months post-stent removal or 6 months post-observation of complete or partial stent migration compared to pain collected at baseline. Baseline for patients without a plastic pancreatic stent immediately prior to study stent placement will be at the time of enrollment. Baseline for patients with a plastic pancreatic stent immediately prior to study stent placement will be at the time of study stent placement.

Pain will be scored between 0 and 100 as the mean of the VAS Pain Score and Frequency of Pain sectors of the Izbicki pain scale.

Complete pain relief is defined as pain score ≤ 10 , and partial pain relief is defined as pain score > 10 and reduced by at least 50% compared to baseline.

August 28, 2017

Boston Scientific
WallFlex Pancreatic Pivotal Protocol
91067616 Rev/Ver AK
Page 19 of 64

Complete or partial pain relief in the setting of a 50% higher average daily narcotic dose will be considered a primary effectiveness endpoint failure. Average daily narcotic dosage for prior month will be assessed at baseline visit prior to plastic or study stent placement, whichever is implanted first, and at 6 months post-stent removal/observation of complete distal migration.

Patients who experience stent migration in setting of recurring pain (VAS Pain Score of ≥ 20) will be considered as having failed the primary effectiveness endpoint.

Patients who are restented in the setting of recurring pain will be considered as having failed both the primary effectiveness endpoint and the secondary endpoint for stricture resolution and may only be restented with a non-study stent.

Restenting with a new study stent may only occur during the initial stent placement procedure for such situations as stent misplacement, improper stent size choice, or other conditions, as necessary and will not be considered a primary effectiveness endpoint failure or a secondary effectiveness stricture resolution endpoint failure.

4.2 Primary Safety Endpoint

Primary Safety Endpoint:

Rate of related SAEs from WallFlex Pancreatic stent placement to end of study.

Relatedness will be determined by the PI, reporting if the SAE is related to the study stenting procedure, to the indwelling study stent, to study stent removal and/or to study stent migration.

Pain thought to be caused by WallFlex Pancreatic stent expansion will be reported, but will not count towards the endpoint if all three of the following conditions apply:

1. Pain can be managed by medication, with the exception of injectable narcotic use for more than 24 hours.
2. Pain does not cause WallFlex Pancreatic stent removal.
3. Pain resolves by 72 hours after WallFlex Pancreatic stent placement.

4.3 Secondary Endpoints

Effectiveness

1. Stricture Resolution

Stricture resolution will be assessed at the time of stent removal or observation of complete or partial stent migration.

Stricture resolution is defined as maintained pain relief without need for restenting or, if pain recurs, confirmation of stent patency adequate for providing drainage of the pancreatic duct.

Restenting with a non-study stent will take place if there is no improvement of clinical status (see definition in secondary endpoint 2 below) and associated persistence of the

August 28, 2017

Boston Scientific
WallFlex Pancreatic Pivotal Protocol
91067616 Rev/Ver AK
Page 20 of 64

stricture based on imaging. Imaging will be conducted per standard of practice and may be prompted by lack of improved clinical status and may consist of non-invasive imaging or pancreatogram. A pancreatogram will only be performed if an ERCP is necessitated for a reintervention with or without restenting.

NOTE: Patients who are restented for recurring pain (VAS Pain Score of ≥ 20) will be considered a failure for stricture resolution and the primary endpoint and may only be restented with a non-study stent.

Restenting with a new study stent may only occur during the initial stent placement procedure for such situations as stent misplacement, improper stent size choice, or other conditions, as necessary and will not be considered a secondary effectiveness stricture resolution endpoint failure or a primary effectiveness endpoint failure.

2. Improved clinical status compared to baseline assessed at each study visit.

Improved clinical status is defined as improvement in at least one and deterioration in none of the following: Pain, Weight and Quality of Life (QOL)

- *Pain: Scored between 0 and 100 as the mean of the VAS Pain Score and Frequency of Pain sectors of the Izbicki pain scale.*
- *Weight is measured*
- *Quality of life: Recorded using SF12*

3. Recurrence of Stricture documented by recurrence of pain with loss of adequate pancreatic duct drainage.

Recurrence of stricture is defined as need for restenting. Restenting will take place if there is deterioration of clinical status (see definition in secondary endpoint 2 above) and documented recurrent stricture based on imaging. Imaging may be prompted by deterioration of clinical status and may consist of non-invasive imaging or of a pancreatogram. A pancreatogram will only be performed if an ERCP is necessitated for a reintervention with or without restenting.

4. Stent Functionality

Stent functionality will be assessed from stent placement until stent removal or observation of complete or partial stent migration.

Stent functionality is defined as adequate pancreatic duct drainage reflected by reduction of pain and lack of restenting.

5. Izbicki pain scale assesed at each study visit

The Izbicki pain scale (see appendix in section 22.1) has four sectors related to severity of pain, frequency of pain, analgesic medication, and disease-related inability to work.

6. Average daily narcotic dose for prior month assessed at each study visit

7. Maintenance of the VAS Pain Score and Frequency of Pain Score recorded at 6 months post-stent removal compared with that recorded at the time of plastic stent removal, for patients with plastic pancreatic stent indwelling immediately prior to study stent placement

August 28, 2017

Boston Scientific
WallFlex Pancreatic Pivotal Protocol
91067616 Rev/Ver AK
Page 21 of 64

Technical Success

8. Ability to deploy the stent in satisfactory position (Stent Placement Success).

Satisfactory position is defined as the stent being across the stricture, without visible occluding impaction at the genu of the pancreatic duct and with distal end of the stent visible in the duodenum. Ease of placement will also be assessed.on a 5 point Likert scale.

9. Successful endoscopic stent removal (Endoscopic Stent Removal Success).

Endoscopic stent removal success is defined as ability to remove stent endoscopically (forceps, snare) without serious stent removal-related adverse events. Ease of removal will also be assessed.on a 5 point Likert scale. Use of stent-in-stent removal technique will be considered a removal failure. If stent migration is noted at time of study stent removal, the patient will be excluded from this endpoint's analysis.

Safety and Device Events

10. Device Events, including findings not associated with adverse events, such as but not limited to asymptomatic stent migration.

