	
Stricture resolution will be assessed at the time of stent removal or observation of complete or partial stent migration.
 
Stricture resolution is defined as maintained pain relief without need for restenting or, if pain recurs, confirmation of stent patency adequate for providing drainage of the pancreatic duct.
 
Restenting with a non-study stent will take place if there is no improvement of clinical status (see definition in secondary endpoint 2 below) and associated persistence of the stricture based on imaging. Imaging will be conducted per standard of practice and may be prompted by lack of improved clinical status and may consist of non-invasive imaging or pancreateogram. A pancreateogram will only be performed if an ERCP is necessitated for a reintervention with or without restenting.
 
NOTE: Patients who are restented for recurring pain (VAS Pain Score of ≥ 20) will be considered a failure for stricture resolution and the primary endpoint and may only be restented with a non-study stent.
 
Restenting with a new study stent may only occur during the initial stent placement procedure for such situations as stent misplacement, improper stent size choice, or other conditions, as necessary and will not be considered a secondary effectiveness stricture resolution endpoint failure or a primary endpoint failure.
 
 2. Improved clinical status compared to baseline assessed at each study visit. 
Improved clinical status is defined as improvement in at least one and deterioration in none of the following: Pain, Weight and Quality of Life (QOL)
 
 • Pain: Scored between 0 and 100 as the mean of the VAS Pain Score and Frequency of Pain sectors of the Izbicki pain scale. • Weight • Quality of life: Recorded using SF12 
 3. Recurrence of Stricture 
Stricture recurrence will be assessed in the subset of patients who had stricture resolution at stent removal or observation of complete or partial stent migration.
 
Recurrence of stricture is defined as recurrence of pain with loss of adequate pancreatic duct drainage requiring restenting. Restenting will take place if there is deterioration of clinical status (see definition in secondary endpoint 2 above) and documented recurrent stricture based on imaging. Imaging may be prompted by

--	---

August 28, 2017

Boston Scientific

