Study Visits and Follow-Up Schedule	
 Baseline Visit: Demographics, Medical History, Symptom Assessment including Pain Score, Concomitant Medications (including injectable narcotics), Average Daily Narcotic Dose, Weight, Quality of Life Score, EPS History, Adverse Events, Imaging (if applicable). If ESWL is deemed necessary at Baseline visit, patient may receive a plastic pancreatic stent placed for 30 to 90 days before study stent placement at the discretion of the Investigator, for example, if there is concern about stone fragments of stone sludge in side branches of the pancreatic duct. WallFlex Pancreatic Stenting Procedure: Pre-stenting pancreatic stone clearance (if applicable), Pancreatic Duct Imaging or other imaging, WallFlex Pancreatic Stent Placement, EPS (if required), Pain Score (prior to stent procedures), Weight, Concomitant Medications (including injectable narcotics), Average Daily Narcotic Dose, Quality of Life, Adverse Events, Plastic Stent Removal prior to study stent placement, as applicable Indwell Follow-up via Telephone or in Person on Month 1 and Month 3: Pain Score, Concomitant Medications (including injectable narcotics), Average Daily Narcotic Dose, Weight, Quality of Life Score, Adverse Events Study Stent Removal(s) intended after 6 months of stent indwell: Pain Score prior to Stent Removal, Concomitant Medications (including injectable narcotics), Average Daily Narcotic Dose, Stent Removal Procedure(s), Weight, Quality of Life Score, Adverse Events, Pancreatic Duct imaging or other imaging to assess stricture resolution Post-Removal Follow-up via Telephone or in Person 3 months after stent removal or observation of complete distal migration: Pain Score, Concomitant Medications (including injectable narcotics), Average Daily Narcotic Dose, Weight, Quality of Life Score, Adverse Events Post-Removal Follow-up via Telephone or in Person 6 months after stent removal or observation of complete distal migration: Pancreatic Duct Imaging or other Imaging, Pain Score, Concomitant Medications (including injectable narcotics), Average Daily Narcotic Dose, Weight, Quality of Life Score, Adverse Events OPTIONAL: If a naso-pancreatic drain is placed after stent removal, then repeated pancreaticographic assessment of stricture resolution at 24 to 72 hours post stent removal. Additional visits as needed

August 28, 2017

Boston Scientific
 WallFlex Pancreatic Pivotal Protocol
 91067616 Rev/Ver AK
 Page 7 of 64

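### When pain recurs, stricture resolution is judged on stent patency, which does not show that the stricture has resolved

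*Combined protocol and SAP*

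**What the plan says.** Section 4.3, item 1, sets the timing: "Stricture resolution will be assessed at the time of stent removal or observation of complete or partial stent migration". The definition then offers two routes in one sentence. The first is "Stricture resolution is defined as maintained pain relief without need for restenting or"; the second is "if pain recurs, confirmation of stent patency adequate for providing drainage of the pancreatic duct". The synopsis (Secondary Endpoints, item 1) carries the same definition.

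Five other texts bear on it:

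- **Restented patients.** A note in both places says that patients restented for recurring pain (VAS of at least 20) "will be considered a failure for stricture resolution and the primary endpoint and may only be restented with a non-study stent".
- **When restenting occurs.** "Restenting with a non-study stent will take place if there is no improvement of clinical status", combined with a stricture that persists on imaging.
- **Imaging.** For the removal visit the synopsis schedules "Pancreatic Duct imaging or other imaging to assess stricture resolution". The section 7.1 table lists duct imaging after removal, with a window of ±4 weeks. The definition of resolution refers to neither.
- **Stent function.** Item 4 is a separate endpoint, assessed while the stent is in place: "Stent functionality is defined as adequate pancreatic duct drainage reflected by reduction of pain and lack of restenting".
- **Recurrence.** The synopsis (item 3) says "Stricture recurrence will be assessed in the subset of patients who had stricture resolution at stent removal" or at observed migration. Section 4.3, item 3, does not repeat this restriction.

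**The concern.** The endpoint is named for the stricture, but its second route tests the device. Section 1.1 argues that success of pancreatic stenting should combine pain with calibration of the stricture. Under the second route a patient can have recurring pain and no demonstrated calibration and still be counted as resolved.

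Two secondary endpoints depend on this. Resolution uses the classification directly, and recurrence is counted among the resolved. A patient who is already in pain could enter the group followed for return of pain. Where no stent remains in the duct, centres have no instruction and could record failure, missing, or their own judgement of the duct.

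**Working it through.** The plan states no figure for this endpoint, so the check sets the texts side by side.

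**1. What stent patency can show at each permitted assessment time**

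- Just before removal: patency can be checked. An open stent shows that the device drains; it also supports the lumen, so it says nothing about the duct without it.
- After removal: no stent is in the duct, so the criterion cannot be applied.
- After complete migration: the same.
- After partial migration: part of the stent may remain and could be checked, but the result again describes the device.

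In every state the criterion is either inapplicable or measures drainage through the stent, which item 4 already covers. The states without a stent are realistic. In the pilot (section 1.2), symptomatic complete distal migration occurred in 3 of 12 placements with intended indwell, 3/12 = 25%.

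**2. Who can be misclassified**

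- Patients with maintained pain relief and no need for restenting use the first route and are not affected.
- Patients restented for recurring pain (VAS of at least 20) are failures and are not affected.
- Patients with recurring pain who are not restented remain. The second route decides their status.

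The restenting rule does not empty this last group. It needs both a lack of improved clinical status and an imaged persistent stricture. Item 2 defines improved status as a gain in any one of pain, weight or quality of life with no loss in the others, relative to baseline. A patient whose pain returns to its baseline level, but no worse, and whose weight has risen therefore counts as improved. That patient does not meet the restenting condition even if imaging shows the stricture, and an open stent would make the patient a resolved case.

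The migration rule in section 4.1 does not close the gap either. Migration with recurring pain is a failure of the primary effectiveness endpoint only; the text does not extend that rule to stricture resolution.

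**3. How an error carries forward**

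Let N be the patients assessed, T those correctly classed as resolved, and m those classed as resolved on an open stent although the stricture persists.

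- Reported resolution is (T + m)/N instead of T/N, an excess of m/N.
- The recurrence denominator is T + m instead of T. If the m patients are later restented, they count as recurrences of strictures that never resolved; if not, they dilute the recurrence rate. The direction of that error is not fixed.

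The opposite error is also possible. A patient with pain after complete migration whose duct is open cannot satisfy the second route, because there is no stent to confirm.

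**4. What is not affected**

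Section 8.1.2 builds the sample size on the two primary endpoints: the larger of 43 and 57, then 57/0.90 = 63.3, rounded up to 64, then 64/0.70 = 91.4, rounded up to 92. Stricture resolution enters none of these steps.

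**The case against.** The strongest reply is that the restenting rules already do the work. A patient with no clinical improvement and an imaged persistent stricture is directed to restenting, and restenting for recurring pain is a failure. A reader might infer from the definition alone that every patient with pain and an open stent is counted as resolved; the documents do not support that. This part of the reply stands and limits the point to patients who are not restented.

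A second reply is that patency is checkable in some patients, since pain is scored before removal and a partially migrated stent may still be in place. That also stands. It shows that the criterion can sometimes be applied, not that it measures resolution.

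A third reply is that the text is probably a slip for patency of the duct or stricture. The stated purpose of the removal-visit imaging makes this plausible. The documents do not say so, however, and the same words appear in the synopsis and in section 4.3.

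Finally, a reader might infer a size from the planning rate: the complement of 75% is 25%, and 0.25 × 92 = 23 patients with pain. This does not hold up. The 75% refers to pain reduction six months after removal or migration, whereas resolution is assessed at removal or migration. Failure of the primary endpoint also includes a higher narcotic dose and insufficient relief without recurrence. The documents do not say how many such patients would have an open stent, nor how many would be restented.

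**Conclusion.** The definition is wrong as written. Its second route does not measure stricture resolution: it cannot be applied once the stent is out of the duct, and it describes the device while the stent is in. Misclassification is confined to patients with recurring pain who are not restented. Its size cannot be derived from the documents, so none is given.

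The reach is two secondary endpoints: resolution, and recurrence through its denominator. That denominator is tied to the resolved subset only in the synopsis. No hypothesis test is attached to either endpoint in section 8.1.2, and a reader should not infer that the primary conclusions are at risk. The conclusion rests on taking the definition literally; if the sponsor meant duct patency, the same correction applies as a clarification.

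**What to change.** In the synopsis and in section 4.3, item 1, replace stent patency in the second route with patency of the treated duct segment or stricture on imaging obtained without the stent. For patients assessed at removal, use the post-removal imaging already scheduled. Because the ±4-week window could be read as allowing images from before removal, state that only images taken after the stent is out count. State in item 3 of both places that the recurrence denominator is this same resolved group.

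For migration found outside the removal visit, the schedule does not guarantee an image at that time; section 7.11 lists duct imaging at additional visits only where applicable. Use that imaging where available. Otherwise report the patient as not assessable by imaging, and give the number so reported.

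The cost is an amendment to the wording of items 1 and 3 in two places, with no new procedure and no change to the restenting rules. The resolution rate may come out lower, and some patients will be unassessable. The first route stays as it is, so the change does not by itself deliver the combination of pain and calibration that section 1.1 describes.

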7.4.3 Average Daily Narcotic Dosage

Average Daily Narcotic Dose for the previous month will be calculated for all study patients at all study visits. The value for this data point will be expressed in units of morphine milligram equivalents (MME).

August 28, 2017

Boston Scientific
WallFlex Pancreatic Pivotal Protocol
91067616 Rev/Ver AK
Page 28 of 64

Site personnel will collect narcotic use information as part of concomitant medication data collection at each visit. Documentation of all narcotic dosage increases and/or decreases throughout the patient's participation will be very important for the accurate calculation of Average Daily Narcotic Dose.

Site personnel will convert all daily narcotic dosages for the previous month to MME. The daily MME values obtained will be added together and divided by the number of days in the previous month to obtain the Average Daily Narcotic Dose. The Average Daily Narcotic Dose value will be rounded to the nearest whole number, if necessary.

Please see Appendix 22.4 for examples of Average Daily Narcotic Dosage calculations.

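### Secondary endpoints 1, 2, 4 and 7 credit a pain score lowered on a raised narcotic dose, which section 4.1 refuses to credit for the primary endpoint

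*Combined protocol and SAP*

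**What the plan says.** The primary endpoint has a narcotic rule (section 4.1, repeated in the synopsis and section 8.1.1): "Complete or partial pain relief in the setting of a 50% higher average daily narcotic dose will be considered a primary effectiveness endpoint failure". The comparison runs between two times. "Average daily narcotic dosage for prior month will be assessed at baseline visit prior to plastic or study stent placement, whichever is implanted first", and again 6 months after stent removal or after complete distal migration is observed.

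Pain relief itself is defined by score alone: "Complete pain relief is defined as pain score" of 10 or less, or, for partial relief, a score above 10 that has fallen by at least half. The score is the mean of the VAS and frequency sectors of the Izbicki scale, so the analgesic sector plays no part.

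Four secondary endpoints in section 4.3 use pain without a dose condition:

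- Endpoint 1: "Stricture resolution is defined as maintained pain relief without need for restenting". Patency has to be confirmed only where pain comes back.
- Endpoint 2: "Improved clinical status is defined as improvement in at least one and deterioration in none of the following: Pain, Weight" and quality of life.
- Endpoint 4: "Stent functionality is defined as adequate pancreatic duct drainage reflected by reduction of pain and lack of restenting". No size of reduction is given.
- Endpoint 7: maintenance of the VAS and frequency scores, for patients who came in with a plastic stent.

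The dose is available throughout (section 7.4.3): "Average Daily Narcotic Dose for the previous month will be calculated for all study patients at all study visits". It is reported as endpoint 6, and the full four-sector Izbicki scale as endpoint 5.

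**The concern.** By writing the narcotic rule into the primary endpoint, the plan accepts that a lower score obtained on much more narcotic is not evidence that the device worked. The secondary endpoints that interpret pain as duct drainage and stricture resolution do not apply that standard. This is a single-arm, pre-approval study, so no control group absorbs the effect of prescribing. A reader of the final report would take the endpoint 1 and endpoint 4 rates as evidence that the stent drains the duct and opens the stricture. Part of those rates could reflect analgesia.

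**Working it through.** **1. The plan's figures.** The point disputes none of them. The primary effectiveness sample size reproduces. With an exact one-sided binomial test of 53% against 75% and n = 43, the null is rejected at 30 or more successes, with P(X ≥ 30 | 0.53) = 0.0190 and power 83.4%. At n = 42 power is 76.6%, and every n checked from 43 to 49 stays above 80%. The safety figure reproduces too: n = 57, reject at 11 or fewer events, alpha 0.0242, power 86.2%. Then 57/(1 − 0.10) = 63.3, rounded up to 64, and 64/(1 − 0.30) = 91.4, rounded up to 92. Hypotheses are stated only for the two primaries, so nothing here depends on how the secondary endpoints are scored.

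**2. The definitions side by side.**

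| Endpoint | Counts as success | Assessed | Dose condition |
|---|---|---|---|
| Primary | Score ≤ 10, or fall ≥ 50% | 6 months after removal or migration | Fails on a 50% higher dose |
| 1 | Relief maintained, no restenting; patency if pain recurs | Removal or migration | None |
| 2 | At least one of pain, weight, QOL better; none worse | Every visit | None |
| 4 | Pain reduced, no restenting | Placement to removal or migration | None |
| 7 | VAS and frequency maintained since plastic stent removal | 6 months after removal | None |

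**3. A hypothetical patient.** Baseline VAS 60 and frequency 75 give (60 + 75)/2 = 67.5. Later VAS 10 and frequency 25 give (10 + 25)/2 = 17.5. The fall is (67.5 − 17.5)/67.5 = 74%. The dose goes from 30 to 60 MME, a rise of (60 − 30)/30 = 100%. Weight and QOL are stable and there is no restenting.

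- With these values through indwell and at removal, endpoints 1 and 4 are met, and endpoint 2 is met at those visits.
- With these values at 6 months after removal, the primary fails on dose and endpoint 2 is met.

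**4. Do the other conditions catch this patient?**

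- *No restenting* is not independent of the score. Under sections 4.3 and 4.6, restenting needs both a lack of clinical improvement and a persisting stricture on imaging. A lowered score is itself an improvement and can keep the trigger from being reached.
- *Imaging* is scheduled at removal, but endpoint 1 needs patency only after recurrence of pain. Masked pain never reaches that branch.
- *Endpoints 5 and 6* describe analgesic use but change no classification.
- *Stratification by narcotic use* (section 8.2.3) covers the primary effectiveness endpoint only.

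Dose increases during indwell are foreseeable: section 4.5 links early removal to pain that medication does not adequately control.

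**5. Size, by assumption.** The documents give no rate of dose increase. If 5%, 10% or 15% of patients had a lower score on a dose at least 50% above baseline, that is 0.05 × 92 = 4.6, 0.10 × 92 = 9.2 or 0.15 × 92 = 13.8 patients. For scale, at an assumed rate of 70% with n = 92 the 95% half-width is 1.96 × √(0.70 × 0.30/92) = 0.094, or 9.4 points. A 10% share could move an estimate by up to about one half-width.

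**The case against.** Six arguments can be made against the point.

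- **Timing.** The primary compares dose at 6 months after removal, whereas endpoints 1 and 4 close at removal or migration, about 6 months earlier. A patient whose narcotics rise only after removal can properly fail the primary and succeed on 1 and 4. This stands. A reader might infer that any patient who is a primary failure and a secondary success exposes a contradiction, and the documents do not support that. The gap is that a dose raised at the secondary endpoint's own assessment time is ignored.
- **Direction.** A reader might also infer that the omission always favours the device. It does not: a patient with unchanged pain on half the dose gets no credit for pain under endpoints 2 or 4.
- **Meaning of a dose increase.** Section 1.1 says pain may have causes other than ductal hypertension, so more narcotic does not prove a persisting stricture. This stands. It is a reason to send such patients to the imaging evidence for endpoint 1 rather than fail them outright.
- **Existing safeguards.** Endpoints 5 and 6 make narcotic use visible, and endpoint 2 requires that weight and QOL do not worsen. Both soften the problem, but neither changes who is counted under 1 or 4.
- **Restenting.** The restenting rules cite the endpoint 2 definition, so a dose condition placed inside endpoint 2 would alter a clinical trigger. This stands, and that definition should not be touched.
- **Undefined cases.** A 50% increase has no clear meaning when the baseline dose is zero. This is already true of the primary, and any extension inherits it.

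**Conclusion.** The point holds as an inconsistency in what counts as pain relief. It bears on how the secondary results are interpreted. Endpoints 1 and 4 can label a patient as resolved and draining on a pain score obtained with a raised narcotic dose, and endpoints 2 and 7 share the gap in part. No test is biased, and type I error and power are unaffected.

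The size is unknown. The counts of about 5, 9 and 14 of 92 rest on assumed shares of 5%, 10% and 15%. A reader might take them as the amount by which the rates are overstated, but they are ceilings. Enrolment of 92 is itself a maximum, and affected patients must also escape restenting. For endpoint 2 they must also show no deterioration in weight or QOL, and some would qualify anyway through a gain in one of those. Endpoint 7 covers only patients with a prior plastic stent, whose number the documents do not give, and it uses a different reference time. The change is worth making because it is cheap.

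**What to change.** **Endpoint 4 and the pain-relief branch of endpoint 1** (section 4.3 and synopsis). State that, for scoring only, reduction or relief of pain does not count when the prior-month average daily narcotic dose at that endpoint's own assessment visit, from Month 3 onward, is at least 50% above the pre-stent baseline dose. Month 1 is left out because its prior-month dose includes the placement procedure. Migration before Month 3 therefore stays uncorrected, and the report should say so.

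**Scoring such a patient on endpoint 1.** Use the patency branch with the duct imaging already scheduled at removal. That branch speaks of stent patency while the scheduled imaging follows removal, so the SAP should say which finding is scored. It should also say how a patient assessed at migration without imaging is handled.

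**Endpoints 2 and 7.** Keep the definitions. Report the results with and without patients whose dose rose by at least 50%. For endpoint 7, take the dose at the study stent placement visit as reference, because the 4.1 baseline precedes the plastic stent.

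**Guard sentences.** State that the clinical-status definition cited by the restenting rules in 4.3 and 4.6 is unchanged. State once, for the primary as well, how a zero baseline dose is read.

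**Cost.** Protocol and SAP wording and minor programming. No new dose data are needed and no sample size changes. Secondary rates may come out slightly less favourable.
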